# 4.7.7. Prohibited medication: Corticosteroid therapy

The use of corticosteroid therapy (IV or oral, chronic or pulse) for post-operative treatment of BA will not be permitted during this trial and will be treated as a protocol violation. Because the published studies to date do not demonstrate a benefit or the safety of corticosteroid therapy following HPE for BA, and because this therapy may have effects that could potentially confound the analysis of the results of this clinical trial, the investigators have agreed not to use this medication for treatment of BA in participants enrolled in this trial. Corticosteroids may be used at the discretion of the treating caregiver for treatment of aseptic meningitis related to the use of IVIG in this protocol, or for other non-BA related indications, such as reactive airways disease, and their use will be recorded on case report forms. Since these are generally short courses of corticosteroids, we do not believe these courses would significantly interfere with the assessment of the study drug so the subject will remain in the study.

# 4.8. Visit Schedule for this clinical trial

Subjects will be evaluated in the outpatient clinic (or in hospital if still in hospital from original HPE surgery) 14 days after HPE, at 30 and 60 days after HPE (at time of IVIG infusions), and then at 90, 180, 270 and 360 days after HPE in the outpatient clinic or during inpatient admissions, or at the time of liver transplantation if before 360 days after HPE. The inclusion of the 14 day time point will allow for careful monitoring for any side effects of the first IVIG infusion. During each visit, information will be captured in the ChiLDREN database. This database will capture data particularly related to the course of BA and to potential adverse effects of IVIG, on the interval medical history, physical findings, diet and medication records, laboratory findings, interval sentinel events, illnesses or hospital admissions, according to the schedule in Table 3 (below).

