#### 4.3.1. **Primary Outcome Measures**:

- 1. Feasibility: Percentage of subjects for whom administration of IVIG is feasible, defined as the successful administration (at least 80% of each dose) of the 3 doses of IVIG at the prescribed times through peripheral IV lines or central lines if already in place for clinical indications.
- 2. Acceptability: Percentage of subjects for whom the study is acceptable, defined as the ability of the subject's family or guardian to allow intravenous line placements, blood draws, and other study procedures for the study subjects.
- 3. Safety and tolerability measures:
  - a. Percentage of subjects with any serious adverse events (SAEs),
  - b. Percentage of subjects with any level 3, 4, or 5 toxicity (per NCI CTEP grading system [http://www.eortc.be/services/doc/ctc/ctcaev3.pdf], and
  - c. Percentage of subjects with other expected adverse events (such as allergic reactions, irritability, fluid volume problems, IV infiltration and aseptic meningitis).

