IVIG will be initiated on day 3-5 after HPE surgery (HPE is day 0) at a dose of 1 gm/kg body weight by slow intravenous infusion over at least 4-8 hours, or according to local clinical guidelines for rate and time of infusion. The same dose (1 gm/kg) and duration of infusion will be repeated on day 30 and on day 60 after HPE. Ideally the first dose will be administered on day 3 after HPE, however the first dose may be administered on day 4 or 5 after HPE if there is a clinical situation that precludes start of the study medication on day 3. Dose #1 must be given while the subject is still hospitalized. Dose #2 and #3 may be given as outpatient infusions at the study site if the subject has been discharged from the hospital, as expected. The dose will be based on the weight of the subject on the day of the infusion. If the subject has an intercurrent illness or infection that would preclude giving the 2nd or 3rd IVIG dose at the specified times, the subject will be stabilized or treated for this illness and then the IVIG will be given if the investigator believes it will be tolerated. Since there is a 10 day window for administering doses #2 and #3 of IVIG, we anticipate that all doses will be able to be given during this window. If dose #2 is missed for reasons other than an IVIG related adverse event, dose #3 may still be given. Standard precautions will be taken for administering IVIG, including administering IVIG in a controlled setting by experienced nursing staff, and with the immediate availability of intravenous diphenhydramine, intravenous or subcutaneous epinephrine, and oral or rectal acetaminophen. Local site standard protocol for administration of IVIG will be followed, which may include premedication with acetaminophen or diphenhydramine.

A single dosage level of 1 gm/kg of IVIG was chosen for this study (rather than a range of escalating doses) because 1) this dose is effective and commonly used to treat other autoimmune or immune-mediated diseases in children and adults, 2) this dose can be administered intravenously over 6-8 hours during an outpatient research visit, and 3) this dose is usually not associated with significant side effects in children. To attempt to study several escalating doses in this study would imply that there was a therapeutic target for serum IgG that we would be trying to achieve and that the proper dose could be determined based on PK/PD studies. However, there is no target serum level of IgG that is

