# 4.7.6. Routine childhood immunizations

It is expected that routine primary immunizations will be given to all children by their primary care provider as recommended by the Committee on Infectious Diseases of the American Academy of Pediatrics (AAP). IVIG has been shown to interfere only with live virus vaccines but not killed virus vaccines. Only killed virus vaccines will be administered to infants under one year of age in this trial. Participants may receive live attenuated viral vaccines at 12-15 months of age (MMR and Varicella vaccinations) because it is very unlikely that substantial amounts of IVIG would still be circulating in the participant at that time. This is based on the last IVIG dose being given 60 days after the HPE procedure, the latter which is expected to be performed at 40 to 100 days of age in the majority of participants with the latest it can be performed in this trial being 180 days of age. The Rotavirus vaccines (live attenuated virus vaccines) are not recommended in children with significant abdominal disorders or following abdominal surgery, and therefore are not recommended for study participants.

Development of infectious diseases and vaccine-preventable diseases Subjects will be prospectively monitored for the development of infectious diseases and vaccine-preventable diseases. Parents and primary care providers of all enrolled subjects will be instructed to contact the study coordinator promptly at the time of any infectious acute illness that leads to visit to the primary care provider, to an emergency department, or if the subject requires hospitalization. An Adverse Event Form will be completed within 24 hrs of each report.

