# Table 3. Schedule of evaluations for the trial of IVIG therapy in infants with BA

Evaluation	Recruitment or Baseline	Initial Admission and initial IVIG infusions	14 days post HPE	30 and 60 days post HPE	90 and 180 days post HPE	270 days post HPE	360 days post HPE	At Liver Trans- plant
Windows for visits		Initial dose to be given on days 3-5 post HPE	±3 days	±5 days	± 20 days	± 20 days	± 30 days	
Informed consent & Eligibility	Х							
Intake/Medical History	X							
Intravenous Infusion of IVIG*		X (dose #1)		X (doses #2 and #3)				
Ursodeoxycholic acid therapy		Х	Х	Х	Х	Х	Х	
Trimethoprim- sulfamethoxasole therapy			Х	x	Х			
Diagnosis and surgery	Х							
Medication Record	Х	Х	Х	Х	Х	Х	Х	X
Physical Exam, Growth Measures	Х	Х	Х	Х	Х	Х	Х	Х
-Complete blood count		X (before IVIG dose #1)	Х	x	Х	Х	х	x
-LFTs, GGT, PT/INR -Electrolytes,	X**	х	Х	х	х	Х	х	x
BUN creatinine		Х	Х	Х	Х	Х	Х	
Research Blood tests - mechanistic studies		X (before IVIG dose #1)		X (before dose #3)	Х		х	
Serum IgG level				X (before dose #3)	Х	Х	х	X prior to TX
Interval Medical History			х	х	Х	х	х	х
Interval Adverse Events		Х	Х	Х	Х	Х	х	Х

\*dose #1, #2, and #3 administered on days 3-5, 30 and 60 post-HPE, respectively, see Section 4.4.4. \*\*May use clinical labs from pre-HPE in not performed post.

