## 7.4. Monitoring and management for specific AEs

Several side effects of IVIG may occur in the subjects during this trial. The following section outlines the plan for monitoring and management of these AEs. This monitoring will be conducted after HPE but before the first dose of study medication is given (to provide baseline data) and then at hospital discharge and at each scheduled follow up visit.

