#### 7.4.4. Aseptic meningitis syndrome (AMS)

AMS may occur infrequently with IVIG treatment. Discontinuation of IVIG treatment has resulted in remission of AMS within several days without sequelae. Administration of corticosteroids may also be helpful, the decision made upon consultation with neurology or infectious diseases specialists. The syndrome usually begins within several hours to two days following IVIG treatment and is characterized by the following symptoms and signs: severe headache, nuchal rigidity, drowsiness, fever, photophobia, painful eye movements, nausea and vomiting. Cerebrospinal fluid (CSF) studies are frequently positive with pleocytosis up to several thousand cells per cu mm, predominantly from the granulocytic series, and with elevated protein levels up to several hundred mg/dL, but negative culture results. Subjects enrolled in this study who exhibit any of these symptoms or signs will have a thorough neurological examination performed including

CSF studies, to rule out other causes of meningitis. Because AMS may occur more frequently in association with high doses (2 g/kg) and/or rapid infusion of IVIG, the risk of AMS will be lowered in this study by using 1 g/kg doses of IVIG and using slow infusion rates. The occurrence of AMS will be an indication to discontinue any further IVIG infusions in the subject.

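### Outcome 3c is at risk of missing non-serious, delayed reactions after IVIG doses 2 and 3, because no adverse-event contact is scheduled for nominally 30 days after either dose

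*Protocol*

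**What the plan says.** Section 4.3.1 makes safety and tolerability a primary outcome. Item 3c is the "Percentage of subjects with other expected adverse events", with allergic reactions, irritability, fluid volume problems, IV infiltration and aseptic meningitis as examples.

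The three infusions are followed differently.

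- **Dose 1** must be given before discharge (Section 4.4.4). Section 4.8 then adds a day-14 visit and gives its purpose: "The inclusion of the 14 day time point will allow for careful monitoring for any side effects of the first IVIG infusion".
- **Doses 2 and 3:** Section 4.4.4 says "Dose #2 and #3 may be given as outpatient infusions at the study site" and anticipates that setting. After day 14, Section 4.8 lists visits "at 30 and 60 days after HPE (at time of IVIG infusions), and then at 90, 180, 270 and 360 days after HPE". The Table 3 footnote fixes the dose days: "dose #1, #2, and #3 administered on days 3-5, 30 and 60 post-HPE, respectively, see Section 4.4.4".

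Section 7.4 ties monitoring for the specific IVIG reactions to a baseline check and "then at hospital discharge and at each scheduled follow up visit". On aseptic meningitis, Section 7.4.4 states: "The syndrome usually begins within several hours to two days following IVIG treatment". Between visits, Section 4.7.6 says that parents and primary care providers "will be instructed to contact the study coordinator promptly at the time of any infectious acute illness" that leads to a primary care or emergency visit, or if the infant needs hospital admission.

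**The concern.** The protocol thought it worth adding a visit to look for side effects of the first infusion, but has nothing equivalent for the other two. For an outpatient infusion, most of the hours-to-two-days onset period falls after the infant has gone home. The protocol names no call, diary or visit in that period, and the stated instruction to report promptly does not extend to irritability, vomiting, drowsiness, rash or a fever that settles at home.

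Two consequences follow. First, non-serious delayed reactions after doses 2 and 3 reach the database mainly through a caregiver's account given weeks later, about an infant who cannot describe headache or photophobia. Second, the first scheduled enquiry after dose 2 is the day-60 visit, which is also the dose-3 visit. Several provisions in Section 7.4 for whether further IVIG is given depend on knowing of an earlier reaction.

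The trial has no concurrent control for safety, so lost events are not offset by similar losses in a comparator. The direction of any error is known even though its size is not.

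**Working it through.** **Inputs.** Dose days and visit windows are from Table 3: dose 1 on days 3-5; day 14 ±3; days 30 and 60 ±5; day 90 ±20. Numbers treated, 23-29, are from Section 5.2.1.

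**Gap from dose to next scheduled adverse-event assessment.** Shortest gap = earliest next visit minus latest dose day. Longest gap = latest next visit minus earliest dose day.

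- Dose 1 to day 14: 11 − 5 = 6 days to 17 − 3 = 14 days; 11 days for a day-3 dose given a visit on day 14. The inpatient stay and discharge check come in addition.
- Dose 2 to day 60: 55 − 35 = 20 days to 65 − 25 = 40 days; nominally 60 − 30 = 30.
- Dose 3 to day 90: 70 − 65 = 5 days to 110 − 55 = 55 days; nominally 90 − 60 = 30.

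Even the shortest gap, 5 days, lies outside the two-day onset period.

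**Number of infusions concerned.** At most 2 × 29 = 58 of 3 × 29 = 87 planned infusions. This is a ceiling on infusions without early post-discharge contact, not a count of missed events.

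**The plan's own figures.** Section 5.2.1 gives the chance of seeing at least one subject with a specific event. The formula is 1 − (1 − p)^n, for n = 23 and n = 29:

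- p = 20%: 99.4% and 99.9% (stated: greater than 98%)
- p = 10%: 91.1% and 95.3% (stated: 91 to 95%)
- p = 5%: 69.3% and 77.4% (stated: 69 to 77%)

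These reproduce. They assume that every event is recorded.

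**Illustration of incomplete capture.** The documents give no capture rate, so the following is an assumption. Let each infusion carry the same independent risk q, with subject-level rate P = 1 − (1 − q)^3. Let a share s of events after doses 2 and 3 be recorded, and all events after dose 1. The observed rate is then 1 − (1 − q)(1 − qs)^2. For P = 10%, q = 1 − 0.9^(1/3) = 0.0345. Observed rate, and chance of at least one recorded case with n = 23 to 29:

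- s = 1: 10%; 91-95%
- s = 0.9: 9.4%; 90-94%
- s = 0.75: 8.4%; 87-92%
- s = 0.5: 6.8%; 80-87%
- s = 0: 3.5%; 55-64%

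For P = 5% and s = 0.5, the observed rate is 3.4% and the chance is 54-63%, against 69-77% stated. The lower values of s are bounds only. They are not plausible for reactions seen during infusion or for serious events.

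**The case against.** A reader might infer that adverse events after doses 2 and 3 are not looked for until weeks later, and that the primary safety percentages are therefore under-counted. The documents do not support that.

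- Every infusion is watched while it runs: for side effects (Section 6.1.5.b), vital signs (7.4.1) and the IV site every 15-30 minutes (7.4.12). IV infiltration, fluid problems and acute allergic reactions are thus mostly seen equally at all three doses.
- Section 7.4.11 says that pulmonary reactions will be monitored after infusions, although it gives no duration or method. Its short onset time for transfusion-related lung injury does not add to the concern.
- Serious events are notifiable within 24 hours of occurrence or identification (7.3). Outcomes 3a and 3b, covering serious and grade 3-5 events, are little exposed.
- Table 3 has an interval adverse-event row at every follow-up visit, so recall is delayed but prompted.
- Irritability as defined in 7.4.2 requires clinical evaluation, so a qualifying outpatient episode has had a care contact.
- The outcomes are counted per subject, so a subject already counted after dose 1 is not lost.
- The day-14 visit itself falls 6-14 days after dose 1. The real protection for dose 1 is the inpatient stay.
- Consent material, local infusion procedures and the manuals of operations are not in view and could contain post-infusion instructions.

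All of this stands, and it narrows the point to non-serious reactions that begin after an outpatient infusion. It does not remove it. A later interval history can recover a remembered episode, but it cannot supply the examination and cerebrospinal fluid studies that Section 7.4.4 calls for at the time, or the contemporaneous confirmation in 7.4.2. An episode managed at home may be recalled without ever becoming classifiable.

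**Conclusion.** The asymmetry is in the text: nominally 30 days without scheduled adverse-event contact after doses 2 and 3 (20-40 and 5-55 days), against an inpatient stay, a discharge check and a dedicated visit after dose 1. The supportable conclusion is that outcome 3c is at risk of under-ascertainment for non-serious, delayed reactions after those two doses.

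It would go too far to state an under-count as fact or to attach a figure to it. The capture figures illustrate sensitivity only and rest on equal, independent risk per infusion. Nor do the documents single out aseptic meningitis as the key reaction: it is one of several expected events and is described as infrequent. The conclusion assumes that doses 2 and 3 are mostly outpatient, as the protocol anticipates, and that no post-infusion contact is set out in material not shown.

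This is an inexpensive improvement to how a primary outcome is measured, and worth making because any loss would favour the trial's hypothesis.

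**What to change.** Add to Table 3 and Section 7.4 a short coordinator telephone contact about 2-3 days after doses 2 and 3, using a fixed checklist of the outcome 3c events. A second call at about 10-14 days, to match the timing of the day-14 check after dose 1, is optional. Extend the prompt-report instruction in Section 4.7.6 from infectious illness to the IVIG reactions listed in Section 7.4. If such contacts already exist in the manuals of operations, a cross-reference in Section 7.4 is enough.

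Cost: a protocol amendment, a one-page checklist and at most 2 × 29 = 58 short calls by existing coordinators (116 with the optional second call). No extra visit, blood draw or staff is needed. The downside is modest coordinator time and a recorded event rate that may look less favourable. No dosing or clinical management rule changes.

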# Table 3. Schedule of evaluations for the trial of IVIG therapy in infants with BA

Evaluation	Recruitment or Baseline	Initial Admission and initial IVIG infusions	14 days post HPE	30 and 60 days post HPE	90 and 180 days post HPE	270 days post HPE	360 days post HPE	At Liver Trans- plant
Windows for visits		Initial dose to be given on days 3-5 post HPE	±3 days	±5 days	± 20 days	± 20 days	± 30 days	
Informed consent & Eligibility	Х							
Intake/Medical History	X							
Intravenous Infusion of IVIG*		X (dose #1)		X (doses #2 and #3)				
Ursodeoxycholic acid therapy		Х	Х	Х	Х	Х	Х	
Trimethoprim- sulfamethoxasole therapy			Х	x	Х			
Diagnosis and surgery	Х							
Medication Record	Х	Х	Х	Х	Х	Х	Х	X
Physical Exam, Growth Measures	Х	Х	Х	Х	Х	Х	Х	Х
-Complete blood count		X (before IVIG dose #1)	Х	x	Х	Х	х	x
-LFTs, GGT, PT/INR -Electrolytes,	X**	х	Х	х	х	Х	х	x
BUN creatinine		Х	Х	Х	Х	Х	Х	
Research Blood tests - mechanistic studies		X (before IVIG dose #1)		X (before dose #3)	Х		х	
Serum IgG level				X (before dose #3)	Х	Х	х	X prior to TX
Interval Medical History			х	х	Х	х	х	х
Interval Adverse Events		Х	Х	Х	Х	Х	х	Х

\*dose #1, #2, and #3 administered on days 3-5, 30 and 60 post-HPE, respectively, see Section 4.4.4. \*\*May use clinical labs from pre-HPE in not performed post.

# 4.9. Surgical procedures and laboratory tests

Results of surgical procedure(s) and laboratory tests performed for the initial diagnosis of BA will be obtained from the medical records and captured as part of the PROBE database. Tests collected at baseline will include hematologic and biochemical analysis (such as complete blood count, liver function tests [including a measurement of total serum bilirubin], prothrombin time/INR, etc). The following laboratory tests will be obtained in all patients, at the time points shown in Table 3, in order to assess study outcomes and for routine clinical care: liver function tests, electrolytes, BUN, serum creatinine, complete blood count, and prothrombin time/INR. These laboratory tests will be performed using standard automated assays in certified clinical laboratories located at each ChiLDREN clinical center.

#### 4.10. Research Blood Tests

The following research tests (see Summary Table below) will be performed on 4.0 ml of blood obtained at time points in Table 3, prior to infusion #1 and #3 of IVIG and at days 90, 180 and 360 post Kasai (except for liver transplant visit). The purpose of these tests is to determine possible effects of the IVIG on the immune system of the treated infant that may provide clues as to its mechanism of action.

- 1. Shipment of 3.0 ml whole blood at room temperature to the laboratory of [name] University of Colorado School of Medicine, Aurora, CO, for isolation of peripheral blood mononuclear cells (PBMCs).
- Flow cytometry studies on PBMCs (see 4.10.1) will include analysis for T-cells, and B-cells, monocyte/macrophages, and neutrophils. These tests will be performed in the laboratory of [name] University of Colorado School of Medicine, Anschutz Medical Campus, Aurora, CO.
- 1.0 ml of blood will be obtained and plasma isolated at local site and stored at -70°C.
- 4. The frozen plasma will be batched and shipped to the CTRC Core Laboratory at Children's Hospital in Aurora, CO for measurement of circulating cytokine levels in plasma by Luminex platform for panel of 13 cytokines (analyzed in the Children's Hospital CTRC Core Laboratory).
- In addition, an aliquot of the frozen plasma(obtained from the CTRC) will be subjected to analysis for anti-enolase antibodies by ELISA in laboratory of [name] at University of Colorado School of Medicine, Aurora, CO.
- 6. Total serum IgG (measured at local site and paid for by this study) obtained before dose 3 and then at follow-up visits.

Test	Volume & type	Processing	Laboratory to perform Assay
Isolation of PBMCs	3.0 ml. whole blood	Aurora, Colorado	[name]
Flow cytometry for CD4, CD8, Tregs, and NK	Isolated PBMCs	None	[name]
Isolation of plasma	1.0 ml. whole blood	Local Site	N/A
Circulating cytokines	150 μL plasma	None	CTRC
Anti-enolase antibodies	100 μL plasma	None	[name]
Total serum IgG	0.4 ml serum (1.0 ml	Local Site	Local Site

blood)	

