# 4.3.2. Secondary Outcome Measures:

- 1. Percentage of subjects who survive 90 days after HPE with both their native liver and serum total bilirubin <1.5 mg/dL at 90 days after HPE. For this study, serum total bilirubin must be measured as a total and not calculated by summing bilirubin components (such as serum indirect plus direct bilirubin or conjugated plus unconjugated bilirubin).
- 2. Percentage of subjects who survive 180 days after HPE with both their native liver and serum total bilirubin <1.5 mg/dL at 180 days after HPE. For this study, serum total bilirubin must be measured as a total and not calculated by summing bilirubin components (such as serum indirect plus direct bilirubin or conjugated plus unconjugated bilirubin).
- 3. Percentage of subjects who survive 360 days after HPE with both their native liver and serum total bilirubin concentration <1.5 mg/dL at 360 days after HPE.
- 4. Percentage of subjects who survive with their native liver at 360 days after HPE.
- Percentage and absolute number of Tregs (CD4+CD25+FoxP3+), CD3/4 T cells, CD3/8 T cells, NK cells (CD56), NK T cells (CD3/56), CD19/20 B cells, macrophages (CD14/11b), and neutrophils; plasma levels of anti-enolase antibody; and plasma cytokine levels (Th1/Th2 multiplex and IL17) prior to IVIG dose #1 and at 60, 90, 180, and 360 days after HPE.

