#### 4.10.1. FACS Analysis of PBMCs

The PBMC flow cytometry analysis will include detailed surface marker expression for the following: T cells, regulatory T cells (Tregs), B cells, moncytes/macrophages, and neutrophils. T cells are defined based on expression of CD3 (present on all T cells), CD4 (helper T cells), CD8 (cytotoxic T cells) and CD56 (natural killer T cells). T cell subset analysis will include the state of the T cells: naïve (CD45RA) versus memory (CD27), and the degree of T cell activation based on CD69 and HLA-DR expression. Tregs are defined based on surface expression of CD4 and CD25 and intracellular expression of FoxP3. B cells are identified based on B cell maturation markers CD19, CD20 and CD27. Monocytes/macrophages are identified based on CD14 expression. One mechanism of action of IVIG includes down regulation of IFN-y Receptor 2 on monocytes, resulting in diminished macrophage activation. Therefore, macrophage expression of IFN- $\gamma$  R2 (CD119) will be determined. Neutrophils are defined based on CD66a and CD16b expression. B cells, macrophages and neutrophils all express the activating  $Fc-\gamma$  receptor (Fc RIII; CD16) and the inhibitory Fc-γ receptor (FcγRIIB; CD32B). IVIG has been shown to down regulate FcyRIII and increase expression of FcyRIIB resulting in inhibition of activation of these cells. Thus, FcyRIII and FcyRIIB expression levels on B cells, macrophages and neutrophils will be determined.

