## Table 5. Total amount of blood drawn from infants in the clinical trial

**NOTE:** Blood volume for clinically indicated tests: Approximately 2.2-3.3 ml of blood may be removed from the child at each visit to evaluate hepatic function, , PT/INR and complete blood count and differential. More may be withdrawn to perform additional clinically indicated lab tests.

At each follow up visit, 0.6 ml of blood will be drawn for a complete blood count and differential, 1.0 ml for hepatic function tests, and 0.6-1.7 ml for a PT/INR. 1.0 ml will be drawn for safety related serum electrolytes, BUN and creatinine. At the initial blood draw prior to IVIG and follow-up visits at 60, 90, 180, and 360 days post-HPE, 4.0 ml of blood will be drawn for mechanistic research studies. An additional 1.0 ml of blood will be drawn at 60, 90, 180, 270 and 360 days post-HPE for serum IgG level.

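### Neutrophil flow cytometry is assigned to isolated mononuclear cells, and neutrophil FcγRIII is read inside a gate that uses the same receptor; neither readout is valid by the stated route

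*Protocol*

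**What the plan says.** The last secondary outcome in Protocol section 4.3.2 begins "Percentage and absolute number of Tregs (CD4+CD25+FoxP3+), CD3/4 T cells, CD3/8 T cells" and runs on to "macrophages (CD14/11b), and neutrophils; plasma levels of anti-enolase antibody". The measurement times are "prior to IVIG dose #1 and at 60, 90, 180, and 360 days after HPE". The list names no specimen, gate or Fc-receptor level for neutrophils.

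Section 4.10 gives the laboratory route. From each draw, 3.0 ml of whole blood is shipped at room temperature to one laboratory "for isolation of peripheral blood mononuclear cells (PBMCs"), and then: "Flow cytometry studies on PBMCs (see 4.10.1) will include analysis for T-cells, and B-cells, monocyte/macrophages, and neutrophils". The summary table in the same section describes the flow assay on isolated PBMCs only as "Flow cytometry for CD4, CD8, Tregs, and NK". It does not mention neutrophils, B cells or monocytes.

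Section 4.10.1, headed as an analysis of PBMCs, says: "Neutrophils are defined based on CD66a and CD16b expression". It then states that IVIG lowers FcγRIII (CD16) and raises FcγRIIB (CD32B), and plans to measure both on B cells, macrophages and neutrophils.

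Separately, Table 3 schedules a complete blood count before dose #1 and at days 14, 30, 60, 90, 180, 270 and 360. Section 4.9 says these laboratory tests serve both study outcomes and routine care. The text with Table 5 adds that at each follow-up visit "0.6 ml of blood will be drawn for a complete blood count and differential".

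**The concern.** There are two separate faults in the stated method.

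The first is the specimen. Neutrophils are polymorphonuclear granulocytes, and isolating mononuclear cells is meant to remove them. Any that remain are contamination, in an amount set by the preparation and possibly by time in transit. A percentage, number or receptor level measured on those cells would not describe the infant's circulating neutrophils, and a change from baseline could reflect handling.

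The second is circular gating. CD16b is a form of CD16. If it helps define the neutrophil population and FcγRIII is then read on that population, cells with the largest loss of receptor are no longer counted as neutrophils. The effect that section 4.10.1 expects is pushed toward no change. A neutrophil number taken from that gate would also fall without any real loss of cells.

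At stake is the interpretation of the neutrophil part of the mechanistic work, and the use of blood from small infants for a readout that would not be valid.

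**Working it through.** The protocol gives no power or precision figure for the biomarkers (section 5.2.3), so there is no stated figure to reproduce. The first three steps compare sections. The fourth is an illustration under assumptions.

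**1. Specimen.** Section 4.3.2 asks for percentage and absolute number of neutrophils. Sections 4.10 and 4.10.1 assign neutrophils to flow on isolated PBMCs. The two do not fit: the cells wanted are those the preparation is meant to discard. The 4.10 summary table, which omits neutrophils, also disagrees with the 4.10 text.

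**2. Is another source scheduled?** The outcome times are pre-dose 1 and days 60, 90, 180 and 360. Table 3 has a complete blood count at all five. A differential is explicit for follow-up visits. Before dose #1 it rests only on the general note under Table 5 about clinically indicated tests at each visit. Table 3 places the count before dose #1 but does not say whether the day-60 count precedes dose #3, as the research draw does. So a valid source exists, but the protocol does not name it for this outcome.

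**3. Reach of the gating fault.** The gate uses CD66a and CD16b, and the readouts are FcγRIII (CD16) and FcγRIIB (CD32B). Only FcγRIII shares a molecule with the gate. B cells and macrophages are identified by other markers, so the circularity does not touch them.

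**4. Size of the gating bias.** Assumptions, none from the protocol: log CD16 intensity is normal with baseline mean 0 and SD 1; the gate keeps cells above a fixed point z; the true fall is d = 1 SD. With φ the normal density and S the upper-tail probability:

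- baseline gated mean = φ(z) / S(z)
- gated mean after the fall = -d + φ(z + d) / S(z + d)
- observed fall = first minus second
- share of baseline-gated cells retained = S(z + d) / S(z)

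Gate at the baseline 5th percentile (z = -1.645):
- baseline mean = 0.1031 / 0.950 = 0.109
- mean after = -1 + 0.3240 / 0.7405 = -0.562
- observed fall = 0.109 + 0.562 = 0.671, so 33% too small
- retained = 0.7405 / 0.950 = 0.78, so 22% of cells seem lost

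Gate at z = -3:
- baseline mean = 0.00443 / 0.99865 = 0.004
- mean after = -1 + 0.0540 / 0.97725 = -0.945
- observed fall = 0.949, so 5% too small
- retained = 0.97725 / 0.99865 = 0.98, so 2% seem lost

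| Gate position | Observed fall (true 1 SD) | Understated by | Cells apparently lost |
|---|---|---|---|
| 5th percentile | 0.67 SD | 33% | 22% |
| 1st percentile | 0.84 SD | 16% | 8% |
| z = -3 | 0.95 SD | 5% | 2% |

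The direction is the same in every row. The size depends almost entirely on a gate position that the protocol does not state.

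**The case against.** The strongest reply is that section 4.3.2 names no specimen and that a blood count is scheduled at every outcome time point, partly to assess study outcomes. A reader might infer from the PBMC route that the listed neutrophil outcome cannot be derived at all, or is unusable for all 29 infants. The documents do not support that. Percentage and number can be recovered from the blood count with differential, subject to confirming the pre-dose differential. What remains is that nothing links the count to this outcome, while 4.10 and 4.10.1 expressly send neutrophils to PBMC flow.

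A reader might also infer that absolute Treg and lymphocyte numbers will be distorted by isolation losses. The protocol never says that absolute numbers come from PBMC yield. Multiplying a flow percentage by the same-visit count is compatible with its text, and section 5.4.3 refers to manuals of operations on sample processing that are not at hand. The gap there is an unstated derivation, not a stated error.

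Neutrophil Fc-receptor levels are not in the 4.3.2 list. They appear only in 4.10.1, so no listed outcome depends on the circular gate unless the neutrophil number is taken from it. Any single figure for the bias also rests on an arbitrary gate.

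Finally, Hypothesis 4 and the Aim 4 analysis in section 5.3 concern Tregs, cytokines and anti-enolase antibody, and that section calls the aim exploratory. This stands and sets the severity.

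**Conclusion.** The concern holds in limited form. By the stated route, neutrophil percentage, number and Fc-receptor levels would describe cells left over from a preparation meant to exclude them. Neutrophil FcγRIII has the further fault that the receptor helps define the population on which it is measured, so a real fall is understated: by about 5% to 33% for an assumed 1 SD fall under a normal model, with gates from z = -3 to the baseline 5th percentile. FcγRIIB suffers from the specimen only.

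The conclusion rests on the ordinary meaning of a mononuclear preparation and on CD16b being a form of CD16. The protocol describes no isolation method for the infants' samples. Severity is minor: the effect is confined to exploratory Aim 4 measures, and no primary, safety or efficacy result is affected. It should still be settled before samples are processed, because neutrophils discarded at isolation cannot be recovered at the analysis stage.

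**What to change.** - **Sections 4.3.2 and 4.10:** name the complete blood count with differential, drawn at the same visit, as the source of neutrophil percentage and absolute number. Confirm that a differential is obtained before dose #1 and that the day-60 count is taken with the research draw before dose #3.
- **Section 4.10:** state that absolute numbers of the other subsets are the flow percentage of the parent population multiplied by that population's count from the same draw.
- **Section 4.10.1:** measure neutrophil FcγRIII and FcγRIIB on a small aliquot of the shipped whole blood, taken before PBMC isolation, with a gate that does not use CD16b (for example CD66a with scatter). Otherwise drop the neutrophil receptor measures. The aliquot would still be shipped blood, so if transit time is thought to affect receptor levels, dropping them is the simpler choice.
- **Section 4.10 summary table:** align the flow cytometry row with the cell types named in the text.

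The cost is wording in three sections and one table, plus one extra stain if the receptor measures are kept. No extra blood is drawn; slightly less of the 3.0 ml remains for PBMC isolation.
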